#### Axial Projection

- Place the cassette near the end of the table and parallel with its long axis.
- Raise the patient's arm on the affected side to a position as near as possible at right angles to the long axis of the body.
- Have the patient lean laterally over the cassette until the shoulder joint is over the midpoint of the film and bring the elbow to rest on the table.
- Flex the patient's elbow 90° and place the hand in the neutral position.

**Confidential**

Protocol Date: May 27, 2013

Amendment 1

Revision 2

**Ascension Orthopedics**

CP-HRA-002

- Have the patient bend his head toward the unaffected side.

Axial Lateral	Axillary Lateral
	Insert Image

### **MRI Instructions**

1.5 TESLA or 3 TESLA MRI can be utilized for the evaluation. The same MRI unit should be used for all evaluations, e.g, the original MRI is performed using a 1.5 Tesla unit all future evaluation for that patient should be performed on the 1.5 Tesla unit.

**Use same series for pre and post operative scans so imaging is comparable**

- **AXIAL T1 :**
  - Resolution 384 x 384 pixels
  - large field of view to include whole scapular body for assessment of glenoid version
  - assess glenoid vault and muscle bulk of spinati
- **AXIAL PD :**
  - Resolution 512 x 512 pixels
  - small field of view to focus on glenohumeral joint region
  - good for PYC on post-op with less artefact
  - good assessment of interface between Pyrotitan and native glenoid on post op

**Confidential**

Protocol Date: May 27, 2013

Amendment 1

Revision 2

**Ascension Orthopedics**

CP-HRA-002

- **2ND AXIAL PD :** **Fat saturated**  
 -Resolution 384 x 384 pixels  
 -small field  
 -better for oedema, cysts etc
- **CORONAL PD :** - good for anatomic detail of cuff, labrum etc
- **CORONAL T2 :** **STIR** (this is by definition fat sat)  
 - less artefact on post op so good for assessing cuff post op
- **SAGITTAL T1 :** **Non fat sat**  
 -muscle atrophy  
 -comparable to Goutallier type assessment of spinati for fatty atrophy
- **SAGITTAL T2 :** **Fat saturated**  
 -good detail and sensitive to fluid around / under prosthesis at bone / prosthesis interface

### **Radiograph / MRI Submission**

The preferred method of radiograph submission is by digital format. The digital images should be saved in JPEG-2000 or dicom format and submitted to the Sponsor on a CD and sent by FEDEX or other over-night carrier. The date of film must either be on the x-ray and designated in the file name. Subjects should be identified by their initials and Subject ID number.

In the event digital images are not available, the site's original radiographs for each x-ray view will be forwarded to the Sponsor. The Sponsor will make digital copies of the original radiographs and return the film copy to the investigational site. All radiographs will be de-identified to the extent possible by the site prior to shipping to the sponsor.

## **6.5 Subject Withdrawals**

### Pre-operative Withdrawal

Subjects who withdraw from consideration prior to signing consent or who decline participation or who sign consent, but are pre-operatively excluded are considered “screen failures” and are not entered as subjects into the study. No forms are required to be maintained at the Site or submitted to the Sponsor for screen failures.

### Intra-operative Withdrawal

If a subject is withdrawn intra-operatively (e.g. inclusion/exclusion criteria, etc.), then a completed Operative Detail CRF must be submitted to the Sponsor in addition to those listed above.

However, all data obtained up until the time of consent withdrawal will be available for analysis. The Withdrawal CRF must be sent to the Sponsor.

### Post-Operative Withdrawal

Subjects withdrawn from the study post-operatively (e.g., withdrawal of consent, etc.) who maintain the investigational components do not require continued follow-up in accordance with the study protocol. However, all data obtained up until the time of consent withdrawal will be available for analysis. The Withdrawal CRF must be sent to the Sponsor.

## **7.0 Revision/Re-operation**

---

Post-operative surgical procedures associated with the operative shoulder are categorized as Adverse Events. If a Subject undergoes any surgical procedure on the operative shoulder in which all of the original Pyro-Titan Resurfacing Shoulder implant components are retained (debridement etc), the Subject is not withdrawn from the study and all follow-up visits are maintained according to the Subject Management Schedule. If the Pyro-Titan Resurfacing Shoulder prosthesis implant is removed then the Subject is considered revised, is withdrawn from the study, an Adverse Event and Study Completion CRFs must

**Confidential**

Protocol Date: May 27, 2013

Amendment 1

Revision 2

**Ascension Orthopedics**

CP-HRA-002

be submitted to the Sponsor. The remaining study-related follow-up visits are not required in the case of revision. Every attempt should be made to retain the explanted device and return it to the Sponsor for evaluation.

## **8.0 Lost To Follow-Up**

---

There may be study subjects who will not or cannot return for follow-up examinations as prescribed in the protocol. These individuals will be considered as non-compliant with the study protocol. This group includes:

- Subjects who refuse to return for follow-up,
- Subjects who relocate without notifying the Sponsor or the Investigator, and cannot be located for continued follow-up arrangements.

Subjects that are considered “lost to follow up” are not considered withdrawn from the study. Sites should make every attempt to contact and schedule post-operative visits. In the event a subject does not respond to telephone correspondences regarding a missed visit, a registered letter should be sent to the subject indicating the importance of the follow-up visits and to contact the office immediately. All correspondence to the subject must be documented within the subject’s source documentation.

## **9.0 Adverse Events**

---

For the purpose of this study, an adverse event is defined as any medical condition or event for which the subject seeks medical attention that, in the physician’s opinion has an association with the medical device or operative procedure. Adverse events may be mild, moderate or severe. All adverse events, device related or procedure related, are transcribed from source documentation onto an Adverse Event CRF and forwarded to the Sponsor (one Adverse Event per CRF).

### **9.1 Serious Adverse Events (SAEs):**

An adverse event that:

- Lead to death;
- Lead to serious deterioration in the health of the subject, that either resulted in:
  - A life threatening illness or injury
  - A permanent impairment of a body structure or a body function
  - In-patient or prolonged hospitalization
  - Medical or surgical intervention to prevent life-threatening illness or injury or permanent impairment to a body structure or a body function
- Lead to fetal distress, fetal death or congenital abnormality or birth defect.

Medical and scientific judgment should be exercised in determining whether an event is an important medical event. An important medical event may not be immediately life-threatening and/or result in death or hospitalization. However, if it is determined that the event may jeopardize the patient and may require intervention to prevent one of the other outcomes listed in the definition above, the important medical event should be reported as serious.

Examples of such events are intensive treatment in an emergency room for a bronchospasm or convulsions that do not result in hospitalization.

This definition of an SAE is not intended to include hospitalization specifically to treat a condition that existed prior to the patient's enrollment in the study (e.g., pre-existing knee injury that is surgically repaired during the study) or prearranged elective surgery performed during this study period.

### **9.2 Unanticipated Serious Adverse Device Effect (USADEs):**

A serious adverse device effect which, by its nature, incidence, severity or outcome has not been identified in the current version of the risk analysis report.

### **9.3 Anticipated Adverse Events:**

As with any type of surgical procedure, there are certain risks or complications associated with shoulder resurfacing. The following list represents the most commonly reported complications and adverse events associated with surgery and shoulder replacement:

**Confidential**

Protocol Date: May 27, 2013  
Amendment 1  
Revision 2

**Ascension Orthopedics**

CP-HRA-002

Potential risks associated with any surgery may include:

- Pain
- Bleeding
- Blood clots
- Infection
- Swelling
- Damage to surrounding blood vessels
- Damage to surrounding tissues or nerves
- Death

Potential risks associated with any shoulder replacement may include:

- Implant loosening
- Implant movement
- Implant wear
- Allergic reaction to wear debris or implant materials
- Implant fracture
- Implant failure (including need to take the implant out)
- Bone fracture
- Shoulder dislocation
- Shoulder pain
- Loss of shoulder function

#### **9.4 Adverse Event Severity Determination:**

All Adverse Events must be classified by the investigator using mild, moderate, or severe to determine the level of severity of the AE as it relates to the evaluation of patient safety through the full course of the AE from initial reporting to the end of study for each patient who participates in this clinical study.

ADVERSE EVENT SEVERITY	
Mild	AE is noticeable to the patient but does not interfere with routine activity and does not require medical treatment.
Moderate	AE interferes with routine activity but responds to symptomatic therapy or rest.

**Confidential**

Protocol Date: May 27, 2013

Amendment 1

Revision 2

**Ascension Orthopedics**

CP-HRA-002

	Usually requires medical treatment.
Severe	AE that results in loss of life or limb.

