# Statistical Analysis Plan

A Multi-center Outcomes Clinical Study of the PyroTITAN™ HRA Shoulder Implant in Humeral Head Resurfacing

Number: CP-HRA-002  
ST: ST1159  
Version: 1.0 05/Oct/2023  
Page: 19 of 19

Events will be summarised by the AE/SAE/ADE/SADE/USADE classifications derived from the Investigator assessment of the event. In the case of disagreements, a separate summary of event classifications made by the Sponsor will also be provided.

In addition, AEs will be summarised by; severity (intensity), relationship to study device, relationship to procedure, outcome and duration of adverse event at trial discontinuation.

A listing will be provided which details subject number, AE description, start date, end date/ongoing, classification, severity, seriousness, relationship to device, relationship to procedure, anticipation, actions taken, outcome and whether study participation was discontinued due to the event.

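### The adverse event severity grades in Protocol 9.4 leave a gap between Moderate and Severe, so the SAP 7.12 severity summary cannot separate events that led to revision or re-operation from events that settled with rest

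*Protocol*

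**What the plan says.** Grading is compulsory. Protocol 9.4 (numbered 9.5 in the table of contents) states: "All Adverse Events must be classified by the investigator using mild, moderate, or severe". It then gives three definitions:

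- Mild: the patient notices the event, but daily life is undisturbed and no treatment is needed.
- Moderate: "AE interferes with routine activity but responds to symptomatic therapy or rest". After a page break the entry continues: "Usually requires medical treatment".
- Severe: "AE that results in loss of life or limb".

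Protocol 7.0 brings re-operations into this scheme: "Post-operative surgical procedures associated with the operative shoulder are categorized as Adverse Events". It also asks for an Adverse Event form when the implant is removed. Protocol 9.0 limits AEs to events that, in the physician's opinion, have a link to the device or the operation ("has an association with the medical device or operative procedure").

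On the analysis side, SAP 7.12 first counts events and subjects by AE, SAE, ADE, SADE and USADE class. It then adds that "AEs will be summarised by; severity (intensity), relationship to study device" and several other attributes. The SAP does not define or redefine the grades. The only departure from the protocol recorded in SAP 7.14 is the 5-year interim analysis.

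**The concern.** A severity scale is useful if each event has one clear place and the order of the grades carries information. Here the middle grade is tied to a response to simple measures, and the top grade is reserved for the most extreme outcome. The complications that matter most for a resurfacing implant, those that end in another operation on the shoulder, lie between the two.

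At stake is the reading of one planned safety summary. If events that needed surgery are recorded as Moderate, that summary puts them in the same row as events that settled with rest. If some sites stretch Severe to cover them and others do not, differences in the table partly reflect site habit. In neither case can a reader use the severity distribution to judge how many events were substantial.

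**Working it through.** No stated figure depends on this point, so the check is mainly textual. Take an AE associated with the device that leads to revision or re-operation, without loss of life or limb, and test it against each definition.

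1. *Must it be graded?* Yes. Protocol 7.0 classes post-operative surgery on the operated shoulder as an AE, and 9.4 requires a grade for every AE.
2. *Mild?* No. Mild excludes any event that needs medical treatment.
3. *Moderate?* Not on its wording. The first sentence requires that the event respond to symptomatic measures or rest, and an event that went on to surgery did not resolve that way. The second sentence describes what is usual for the grade. It makes Moderate a plausible home for treated events but does not remove the condition in the first.
4. *Severe?* No, by construction of the example.

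The uncovered region is therefore any event that interferes with activity, does not respond to symptomatic measures, and stops short of losing life or limb. The protocol expects such events. Section 9.3 lists implant fracture, implant failure with removal, bone fracture and dislocation among the potential risks. Section 12.0 says complications can be treated by conversion to another arthroplasty or by fusion.

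*What would fill the Severe row?* On literal use, deaths and limb loss only. Section 12.0 describes fatal complications as very rare. Section 16.0 asks for each death to be documented on the Adverse Event/Withdrawal form. Over ten years the row could therefore hold some deaths, possibly including deaths unrelated to the device, but not revisions as such.

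*Scale, for illustration only.* Inputs: 387 planned subjects and a 96.1% reference success rate (Protocol 11.3), and the 3.3% non-inferiority margin (Protocol 11.3, SAP 7.9).

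- Expected composite failures = N × (1 − success rate) = 387 × (1 − 0.961) = 387 × 0.039 = 15.1, about 15 subjects.
- At the non-inferiority limit, 96.1% − 3.3% = 92.8%, so 387 × 0.072 = 27.9, about 28 subjects.

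These are failures of the composite: removal or revision, device-related complications needing surgical replacement, removal or augmentation, or chronic dislocation. The documents give no split among them and no follow-up time for the 96.1%.

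**The case against.** The strongest reply is that nothing important is lost. Removal and revision are part of the primary composite. Infection, loss of fixation, breakage, dislocations and revisions are named safety endpoints (SAP 5.4). The seriousness definition in Protocol 9.1 covers in-patient hospitalisation and qualifying surgical intervention, so many of these events will appear in the SAE or SADE counts. The AE listing in SAP 7.12 shows severity, seriousness and actions taken for each event, so a reader can find a Moderate event that was revised. No hypothesis or success rule uses severity. All of this stands, and it limits the point to one supplementary summary. It does not repair that summary, because seriousness is a separate attribute and SAP 7.12 describes no cross-tabulation of the two.

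A second reply is that the second sentence of Moderate already accommodates treated events. This is partly right and explains why sites would probably choose Moderate. It leaves the first condition unmet.

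A reader might infer more than the documents support:

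- *That these events would go ungraded.* Grading is compulsory, so the field will be filled. The problem is the absence of a fitting definition.
- *That sites are bound to use Moderate.* The text does not say so, and inconsistent grading is equally possible.
- *That the study as a whole will understate the device's risk.* It will not, given the other outputs listed above.
- *That about 15 revisions would be misgraded.* The 15 counts all composite failures, with no breakdown by type.

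The table shells named in SAP section 2 are a separate document, and the case report forms are not in the material reviewed. Either may add a cross-tabulation or further grading guidance that cannot be seen here.

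**Conclusion.** The gap is real on the text, and it is minor. Followed as written, the plan gives a severity summary that cannot distinguish events leading to revision or re-operation from events that settled with simple measures, with a Severe row containing little beyond deaths. The effect is confined to that summary. The primary endpoint, the safety endpoints, the seriousness-based counts and the listing are unaffected.

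The conclusion assumes that investigators apply the definitions in 9.4 broadly as worded, and that neither the case report form nor the table shells supply a different scale. The figures of about 15 and 28 subjects indicate only the order of magnitude of device failures. They do not estimate the number of misplaced events.

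**What to change.** For events still to be graded, reword Protocol 9.4 so that the three grades cover every event. For example, extend Severe to include events that prevent routine activity or lead to surgical intervention, as well as those already covered. Record which definition applied to each event, so that the two scales are not pooled unnoticed.

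For events already recorded, which may be many given a 2013 protocol and an October 2023 SAP, leave the investigator's grade as the reported severity. In SAP 7.12:

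1. State the 9.4 definitions beside the severity summary, with a note on the gap.
2. Add a cross-tabulation of severity by seriousness and by whether surgical action was taken. A supplementary derived category would also serve, shown next to the investigator's grade and not in place of it.

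Severity, seriousness and actions taken are already planned for the AE listing, and SAP 7.4 already uses a date of surgical intervention, so no new site data should be needed. If the actions-taken field does not code surgery, that date can help identify the events.

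The cost is a wording change handled under Protocol section 20.0, one extra table and perhaps one derived variable. The visible consequence is that more events will be shown as having needed surgery.

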### **9.5 Adverse Event Reporting:**

Investigators and /or study staff are required to report AEs (and all reportable effects) per their Institutional Review Board/Ethics Committee Standard Operating Procedures.

In the event of a complication, the Investigator and/or other professional personnel in attendance will undertake the appropriate therapy. All adverse signs and symptoms (device or procedure related) that occur during the study are to be recorded on an Adverse Event CRF. The description of adverse events will include cause, date of initial onset, severity, treatment, and date of resolution.

All serious and non-serious device or procedure related adverse events and unanticipated serious adverse device effects that occur during this investigation must be reported in a timely manner by the Investigator using either telephone or fax to:

ATTN: Clinical Research  
Ascension Orthopedics, Inc

**[contact]**

#### **INCIDENT:**

Any malfunction or deterioration in the characteristics and/or performance of a device, as well as any inadequacy in the labelling or the instructions for use which, directly or indirectly, might lead to or might have led to the death of a patient, or USER or of other persons or to a serious deterioration in their state of health."

A serious deterioration in state of health can include:

- a) Life-threatening illness
- b) Permanent impairment of a body function or permanent damage to a body structure
- c) A condition necessitating medical or surgical intervention to prevent a) or b)

(Examples: - Clinically relevant increase in the duration of a surgical procedure

**Confidential**

Protocol Date: May 27, 2013

Amendment 1

Revision 2

**Ascension Orthopedics**

CP-HRA-002

- A condition that requires hospitalisation or significant prolongation of existing hospitalisation)

d) Any indirect harm as a consequence of an incorrect diagnostic or IVD test results when used within manufacturer's instructions for use

e) Foetal distress, foetal death or any congenital abnormality or birth defect

*Notification:*

As the product is CE marked and used in its intended purpose, Medical Device vigilance system applies: The Investigator should report incidents with Medical Device to the manufacturer or to the National Competent Authority, depending on national practice.

## **10.0 Termination of Subject Participation**

---

Any subject who wishes to withdraw from this clinical investigation on his/her own accord and for whatever reason is entitled to do so without obligation and prejudice to further treatment. In addition, the Clinical Investigator may decide for reasons of medical prudence (e.g. stroke, amputation), to withdraw a subject. In either event, the Clinical Investigator will clearly document the date and reason(s) for the withdrawal on the Withdrawal CRF. The investigator should note if the withdrawal was related to the device.

## **11.0 Statistical Methods**

---

### **11.1 Purpose**

This is an exploratory study intended to provide data that may be mined for a variety of purposes. The treatment of shoulder pathology with a prosthesis is an area where there is still a great deal to learn. There is no consensus, for example, regarding when a resurfacing is preferred to a total shoulder or hemi arthroplasty in subjects with an intact glenoid.

Accordingly, the study is designed to allow comparisons to these implants either through literature review or other clinical data mined from outcome studies of other implant

**Confidential**

Protocol Date: May 27, 2013

Amendment 1

Revision 2

**Ascension Orthopedics**

CP-HRA-002

configurations. The number of shoulders available must be adequate in number to follow outcomes in the long term, accounting for expected attrition, and in accordance with peer reviewed journal standards.

## **11.2 Study Design**

This clinical investigation is a prospective, non-comparative, multicenter, post market study designed to monitor the clinical safety and performance of the PyroTITAN™ HRA Shoulder prosthesis. Results will be contrasted with results from the literature.

## **11.3 Sample Size and Power Analysis**

The original sample size in this study was 150 enrolled subjects. Additional proof testing and improvements in the device inspection process were employed during the study, at which time it was determined that an additional cohort of subjects was necessary. We are now comparing a cohort of subjects enrolled after these changes to the original cohort of subjects.

With an expected attrition rate of 10% per annum, this will yield an evaluable sample size of 52 shoulders at ten years ( $150 * 0.9^{10} = 52.3$ , where 0.9 or 90% is the number expected to be retained from one year to the next). Based on past experience, we may obtain clinical follow-up on this number of shoulders, but we may obtain radiographic follow-up on as few as two-thirds of these shoulders (about 35 shoulders). This remaining number of evaluable shoulders with clinical and radiographic follow-up is adequate to establish a reliable ten-year survival estimate of survival for hemi arthroplasty (Dorey and Amstutz, 1986).

For the new cohort, the sample size is calculated based on the non-inferiority of the study device. The success rate for the study device is 96.1% from the original population and is used as reference rate. Therefore, for a conservative success rate of 96.1% of the study device is used in the study. The non-inferiority margin  $\delta$  of -0.033 is chosen in the study. 212 subjects are required to achieve  $100(1 - \beta) \% = 80\%$  power to detect non-inferiority at the Significance level of  $\alpha = 0.05$ . To account for 10% lost to follow-up, the

total number of additional subjects is 237. Therefore, the estimated enrollment for the study will be 387 subjects.

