# 6 STATISTICAL CONSIDERATIONS

## 6.1 Determination of Sample Size

The following is the sample size justification taken from the study protocol V2, 27-May-2013:

The original sample size in this study was 150 enrolled subjects. Additional proof testing and improvements in the device inspection process were employed during the study, at which time it was determined that an additional cohort of subjects was necessary. We are now comparing a cohort of subjects enrolled after these changes to the original cohort of subjects.

With an expected attrition rate of 10% per annum, this will yield an evaluable sample size of 52 shoulders at ten years ( $150 * 0.9^{10} = 52.3$ , where 0.9 or 90% is the number expected to be retained from one year to the next). Based on past experience, we may obtain clinical follow-up on this number of shoulders, but we may obtain radiographic follow-up on as few as two-thirds of these shoulders (about 35 shoulders). This remaining number of evaluable shoulders with clinical and radiographic follow-up is adequate to establish a reliable ten-year survival estimate of survival for hemi arthroplasty (Dorey and Amstutz, 1986).

For the new cohort, the sample size is calculated based on the non-inferiority of the study device. The success rate for the study device is 96.1% from the original population and is used as reference rate. Therefore, for a conservative success rate of 96.1% of the study device is used in the study. The non-inferiority margin  $\delta$  of -0.033 is chosen in the study. 212 subjects are required to achieve  $100(1 - \beta) \% = 80\%$  power to detect non-inferiority at the Significance level of  $\alpha = 0.05$ . To account for 10% lost to follow-up, the total number of additional subjects is 237. Therefore, the estimated enrolment for the study will be 387 subjects.

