### 7.9 Analysis of Primary Endpoint(s)

A composite endpoint for Clinical success (device survival) is defined as a binary variable (1/0) (1 if all the following are true and 0 if any is false):

- A. Device remains implanted.
- B. Absence of device-related complications requiring surgical replacement, removal, or augmentation of components.
- C. Freedom from chronic dislocation.

The primary endpoint is the clinical success (device survival) rate at 10-years.

The study hypothesis is to test whether the 10-year survival (i.e., clinical success) rate in the investigational PyroTITAN HRA group is non-inferior to the reference rate at 96.1%. This study will be considered successful if the upper bound of the two-sided 95% confidence interval for the success rate difference (reference – study survival rate) is less than the non-inferiority margin of 3.3%.

The primary non-inferiority hypothesis is formulated as:

$$H_0: P_0 - \delta \geq P_T$$

$$H_a: P_0 - \delta < P_T$$

The variables are defined as follows:

$P_T$  = 120-month success rate in the PyroTitan HRA group

$P_0$  = Reference success rate from original population

$H_0$  = Null hypothesis

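### The new cohort is sized for a single 10% loss while the same section expects 10% per year, so the stated 80% power is not expected at the SAP's 10-year test

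*Protocol*

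**What the plan says.** Protocol section 11.3 sizes the study in two parts, and SAP section 6.1 reproduces the text as taken from the protocol.

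- Original cohort of 150: "With an expected attrition rate of 10% per annum, this will yield an evaluable sample size of 52 shoulders at ten years". The section prints the compounding, 150 × 0.9^10 = 52.3.
- New cohort: "The success rate for the study device is 96.1% from the original population and is used as reference rate", with a margin of 3.3 percentage points, 80% power and alpha 0.05 (sidedness not stated). The result is given as "212 subjects are required to achieve" that power. Then: "To account for 10% lost to follow-up", the "total number of additional subjects is 237". This 10% has no time unit. Adding 150 gives the total of 387.

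Protocol section 5.1 has all 387 followed for 10 years. Protocol section 11.7 evaluates clinical success at 24, 60 and 120 months. SAP section 7.9 settles on the last of these: "The primary endpoint is the clinical success (device survival) rate at 10-years". It tests that rate for non-inferiority to 96.1%, with the FAS (all enrolled subjects, so both cohorts pooled) as the primary population. The new cohort alone appears only as a per-protocol subgroup in an additional summary.

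**The concern.** Both cohorts receive the same device, follow the same visit schedule and are observed for the same 10 years. One is expected to lose 10% of its remaining subjects every year, the other 10% once. Nothing in either document explains why the second cohort should be retained so much better.

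The figures 212, 237 and 80% are the only sizing behind the non-inferiority claim. If the yearly rate is the real expectation, the 80% does not describe the test that SAP 7.9 specifies at 10 years. A failed or borderline result could then be read as coming from a study that was large enough to settle the question.

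**Working it through.** **Inputs.** Success rate 96.1%, margin 0.033, power 80%, alpha 0.05, 212, 237, 387, and the 10% and 10%-per-year losses, all from Protocol 11.3 (repeated in SAP 6.1). The 10-year test and the primary population come from SAP 7.9.

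**Step 1: reproduce 212.** Neither document prints a formula. The one that gives 212 is a one-sample comparison with a fixed reference, with the variance taken at the assumed rate and alpha one-sided:

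n = p(1−p)(z_0.95 + z_0.80)² / margin² = 0.961 × 0.039 × (1.645 + 0.842)² / 0.033² = 212.8 (with unrounded z values).

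**Step 2: reproduce 237.** 213 / 0.9 = 236.7, so 237. (212 / 0.9 = 235.6 would give 236.) The 10% was therefore applied once. At 10% per year it covers only the first year: 237 × 0.9 = 213.3.

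**Step 3: reproduce 52.** 150 × 0.9^10 = 52.3, as printed.

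**Step 4: apply the yearly rate to both totals.**

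| Month | Factor | New cohort (237) | FAS (387) |
|---|---|---|---|
| 24 | 0.9^2 = 0.8100 | 191.97, about 192 | 313.47, about 313 |
| 60 | 0.9^5 = 0.5905 | 139.95, about 140 | 228.52, about 229 |
| 120 | 0.9^10 = 0.3487 | 82.64, about 83 | 134.94, about 135 |

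Conversely, keeping 212 of 237 for ten years requires a yearly loss of 1 − (212/237)^(1/10) = 1.1%, about one ninth of the stated rate.

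**Step 5: power on the Step 1 formula** (96.1% against 92.8%). Power = Φ(√n × 0.033 / √(0.961 × 0.039) − 1.645) = Φ(0.1705√n − 1.645).

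- n = 213: 0.80, which matches the plan.
- New cohort, 24 months, n = 192: Φ(0.72) = 0.76.
- New cohort, 120 months, n = 83: Φ(−0.09) = 0.46.
- FAS, 120 months, n = 135: Φ(0.34) = 0.63.
- FAS at 24 and 60 months: n exceeds 212, so power on this formula is above 80%.

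Only the loss assumption is varied here. SAP 7.9 refers to a two-sided 95% interval, which corresponds to one-sided 2.5%. On that basis the same formula gives about 34% (n = 83) and 51% (n = 135). That mismatch in alpha is a separate matter.

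**The case against.** The strongest case on the other side has four parts.

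**The time point for 212 is not stated.** Protocol 11.3 does not tie it to 10 years, and Protocol 11.7 lists three time points. A 96.1% rate quoted in a protocol dated May 2013, for a device CE marked in November 2009, can hardly be a 10-year rate, so 212 may have been meant for an early visit. This is an inference, but a fair one. At 24 months the new cohort's shortfall is small: 192 against 212, and about 76% power. What remains is that the SAP places the test at 10 years while repeating the sizing unchanged.

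**The primary population is the pooled FAS.** A reader might infer that 83 and 46% describe the primary analysis, or that the shortfall appears whichever analysis set is used. The documents do not support either. The FAS stays above 212 at 24 and 60 months and falls below it only at 120 months, where about 135 and 63% apply.

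**The plan makes no explicit promise.** A reader might also infer that it states 237 will leave 212 evaluable at the 10-year endpoint. No sentence says so. It says that 212 are required and that 237 allow for 10% loss.

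**Lost subjects are not without information.** Subjects revised early are known failures, and SAP 7.9 provides Kaplan-Meier estimation with censoring. This stands in part: the counts above are of subjects followed to the visit, not of all the information. However, Kaplan-Meier is planned only if the data permit, while the success criterion rests on a rate with an exact interval, and SAP 7.3 has data analysed as observed.

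The yearly rate is also written for the original 150, so applying it to the new cohort is an inference. Neither document gives any other yearly rate or a reason for a lower one. Finally, the protocol calls the study exploratory, but SAP 7.9 sets a formal success criterion.

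**Conclusion.** The inconsistency is real and the plan is wrong as written. One section uses two incompatible loss assumptions, and at the yearly rate it states, the 80% power is not expected at the 10-year test: about 63% for the FAS and 46% for the new cohort alone.

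These sizes rest on three assumptions: 10% per year applies to both cohorts, the Step 1 formula is the one the plan used, and only subjects followed to 120 months count. Using partial follow-up would improve on them by an amount that the documents do not allow to be calculated. The finding concerns the stated sizing. It does not show that every analysis set or time point falls short, and it is not a case for enlarging the study.

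**What to change.** Because SAP 6.1 presents its text as taken from the protocol, leave that text intact and add a note after it. Amend Protocol 11.3 only if it is reopened. The note should:

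- state one attrition assumption for both cohorts;
- name the time point to which 212 and 80% apply;
- say that at 10% per year the 80% power is not expected at 120 months;
- restate the expected power or confidence-interval width at 120 months for the FAS and for the new cohort, using actual follow-up where it is known.

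If 10% in total over ten years is what is meant, state that for both cohorts and correct the 52.

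The cost is one short note and a recalculation. The only downside is a less favourable stated power.
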